10.3 Analysis Datasets

Participants who complete all follow-up visits will be included in the study.

CONFIDENTIAL

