IDE for the purpose of this study was obtained from the FDA (IDE approval # G190316. Approval letter provided [attachment 2].

FDA documents of the device under investigation for approved indications and device DFU are attached to this IRB protocol [attachments 3,4].

FDA reviewed the supplement of IDE application to expand study for significant risk device proposing the addition of 21 patients. FDA has determined sufficient data to support expansion of human clinical trial; this means there are no subject protection concerns that preclude expansion of the investigation. Approved to expand study. Limit 1 US institution and 50 US subjects. [attachment G190316-S003. Letter.EPEX.APPR]

CONFIDENTIAL

This material is the property of the NYU School of Medicine and Langone Medical Center. Do not disclose or use except as authorized in writing by the study sponsor
Interventional Template Version: 12 February 2020

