5.5 Duration of Study Participation

Each subject will be enrolled in the study for approximately 13 months from the initial screening visit (visit 1; Day -30) until the last follow-up visit at 12 months post intervention (visit 7; Day 360).

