5.7 Participant Withdrawal or Termination

5.7.1 Reasons for Withdrawal or Termination

Participants are free to withdraw from participation in the study at any time upon request. Participation of a patient in this clinical study may be discontinued for any of the following reasons:

- The patient withdraws consent or requests discontinuation from the study for any reason;
- Occurrence of any medical condition or circumstance that exposes the patient to substantial risk and/or does not allow the patient to adhere to the requirements of the protocol;
- Any AE, clinically significant adverse event, severe laboratory abnormality, intercurrent illness, or other medical condition that indicates to the investigator that continued participation is not in the best interest of the patient;
- Pregnancy during study period;

CONFIDENTIAL

- Patient failure to comply with protocol requirements or study-related procedures;
- Termination of the study by the Sponsor, the regulatory authority, FDA, or IRB.
- The participant meets an exclusion criterion (either newly developed or not previously recognized) that precludes further study participation
- Progression of osteoarthritis requiring surgical therapy
- Patients found to have osteonecrosis on pre-procedural MRI

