5.7.2 Handling of Participant Withdrawals or Termination

If a patient withdraws prematurely from the study due to the above criteria or any other reason, study staff should make every effort to complete the full panel of assessments scheduled for the follow-up visits. The reason for patient withdrawal must be documented in the electronic case report form (eCRF). In the case of loss of follow-up, attempts to contact the patient will be made and documented in the patient's medical records. Every effort will be made to undertake protocol-specified safety follow-up procedures to capture AEs, serious adverse events (SAEs), and unanticipated problems (UPs).

Withdrawn patients can be replaced.

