7.3.4.4 Follow up visit at 12 months (Visit 7, Day 360 +/- 10)

- Obtain medical history
- Record adverse events as reported by participant or observed by investigator (if applicable)
- Targeted physical exam
- Administration of study questionnaires
- Previous / concomitant treatments, including medical history
- Peripheral venous blood draw and urine sample to perform follow-up laboratory tests
- Note: Subjects will be required to withhold pain medications 24 hours prior to screening and each visit for the evaluation of pain

7.3.5 Follow up visit at 18-48 month (visit 8):

- This visit is optional to all study participants who completed 12 months visit by August 31, 2024 and fall within 18-48 months window from the date of procedure. This visit is not expected to add significant risk to participant and will only occur after obtaining informed consent from participants. This visit is important to add at this point of the trial to obtain long term follow up data.
- Obtain medical history
- Record adverse events as reported by participant or observed by investigator (if applicable)
- Targeted physical exam
- Administration of study questionnaires
- Previous / concomitant treatments, including medical history
- Peripheral venous blood draw and urine sample to perform follow-up laboratory tests
- Note: Subjects will be required to withhold pain medications 24 hours prior to screening and each visit for the evaluation of pain

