10.2 Statistical Hypotheses

This is a single arm study (i.e., no sham, placebo or alternative treatment included). The primary objective (clinical success rate) is a binary assessment of whether or not each patient shows at least a 50% reduction in WOMAC pain scores from baseline (pre-treatment) to post-treatment follow-up at 3 months.

The study is designed to test the null hypothesis (H_0) that the true proportion (PT) of patients that will manifest a positive treatment response, is no greater than 0.5 against the one-sided alternative hypothesis (HA) that $PT \geq 0.75$. The null hypothesis will be rejected and it will be concluded that the treatment is worthy of further investigation if at least 16 of the 23 patients show a positive response to treatment.

The response rate will be summarized in terms of the observed proportion of patients manifesting a positive response and a two-sided exact 95% confidence interval (CI) per the Blyth-Still-Casella method (31). The treatment will be declared a success if the data support the conclusion that at least 75% of treated patients can be expected to show a positive response. The treatment will be considered unworthy of additional study without further development if the data are consistent with the conclusion that no more than 50% of treated patients can be expected to show a positive response.

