10.4.2 Analysis of the Primary Endpoint(s)

The primary endpoint is the clinical success rate defined as at least 50% reduction in WOMAC pain score at 3-month follow-up compared to baseline as a binary assessment.

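### The only analysis set is patients who complete all follow-up, so the 3-month primary endpoint depends on attendance to month 12 and is likely, though not certain, to be biased upward

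*Combined protocol and SAP*

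**What the plan says.** Section 10.3 is one sentence: "Participants who complete all follow-up visits will be included in the study". No other analysis set is defined. Section 10.1 says that no formal SAP will be prepared before database lock, so no later document is planned that would add one.

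Section 10.4.2 sets the endpoint: "The primary endpoint is the clinical success rate defined as at least 50% reduction in WOMAC pain score at 3-month follow-up compared to baseline". The Protocol Summary and Section 5.5 place the last follow-up visit at 12 months (visit 7, Day 360). Section 7.3.5 adds visit 8 at 18 to 48 months: "This visit is optional to all study participants who completed 12 months visit by August 31, 2024".

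Section 5.7.1 lists reasons for discontinuation. They include "Progression of osteoarthritis requiring surgical therapy" and adverse events that lead the investigator to judge continuation unsuitable. They also include pregnancy, non-compliance and osteonecrosis found on the pre-procedural MRI. Section 5.7.2 adds, without limiting it by reason or timing: "Withdrawn patients can be replaced". The same section asks staff to try to complete the follow-up assessments in patients who withdraw, and Section 7.3.6 provides an early-termination visit with questionnaires.

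Section 10.2 tests a null success rate of at most 0.5 against 0.75 and words its conclusion in terms of treated patients. Accrual is 50, to yield 40 (Sections 4.1 and 5.6). Section 2.2 reports the FDA's condition: "Limit 1 US institution and 50 US subjects".

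**The concern.** Whether a patient counts in the 3-month analysis depends on what happens in the nine months after the endpoint is measured. Someone with a complete 3-month WOMAC score who misses month 12 disappears from both numerator and denominator. The result then describes completers, while the stated conclusion is about everyone treated.

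The selection is unlikely to be neutral. Progression to surgery and adverse events are reasons to leave that plausibly go with poor pain response, and a treated patient who leaves may be replaced by a new one. The data that Sections 5.7.2 and 7.3.6 ask for at withdrawal would help, but no rule brings them into the analysis. There is no control arm to share the bias.

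At stake are the estimated success rate and the 5% error rate of the test that decides whether the treatment merits further study.

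**Working it through.** **Inputs from the protocol.** Null rate 0.50, alternative 0.75, one-sided 5% level, 80% power, rule of at least 16 of 23 (Sections 10.2 and 10.5); 20% attrition, 40 evaluable of 50 accrued (Sections 4.1, 5.6 and 10.5).

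**Step 1: reproduce the stated design.** Exact binomial tails give P(X ≥ 16 | 23, 0.50) = 0.0466 and P(X ≥ 16 | 23, 0.75) = 0.8037. The plan states 0.047 and 80.4%, so both agree. Enrolment also agrees: 23/0.8 = 28.75, rounded up to 29, and 40/0.8 = 50.

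**Step 2: a cut-off for n = 40.** The plan gives none. I assume the smallest count with exact one-sided alpha of at most 0.05. P(X ≥ 25 | 40, 0.50) = 0.077 is too large and P(X ≥ 26 | 40, 0.50) = 0.040 qualifies, so the assumed rule is 26/40.

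**Step 3: effect of removing non-completers.** Let p be the true 3-month success rate in all treated patients, d the share removed and q the success rate among those removed. The completer rate is

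s = (p − d·q) / (1 − d).

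The protocol gives no q, so I show a range. With p = 0.50 (the null boundary), d = 0.20 and 40 analysed:

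| q | s | P(X ≥ 26 of 40) |
|---|---|---|
| 0 | 0.50/0.80 = 0.625 | 0.44 |
| 0.25 | 0.45/0.80 = 0.5625 | 0.17 |
| 0.40 | 0.42/0.80 = 0.525 | 0.076 |
| 0.50 | 0.40/0.80 = 0.500 | 0.040 |
| 0.75 | 0.35/0.80 = 0.4375 | 0.006 |

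With d = 0.10 and the rule held at 26/40, q = 0 gives s = 0.50/0.90 = 0.556 and a false-positive rate of 0.15; q = 0.25 gives s = 0.475/0.90 = 0.528 and 0.08.

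The bias is upward when q is below the completer rate, zero when they are equal, and downward when q is above it.

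**Step 4: cost of the strictest alternative.** Suppose every missing 3-month score in 50 treated patients counts as failure. The exact cut-off is 32/50 (alpha 0.032), with power 0.971 at a true rate of 0.75 if nothing is missing. If a share m is missing for reasons unrelated to outcome, the apparent rate is 0.75(1 − m):

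- m = 5%: 0.7125, power 0.90
- m = 10%: 0.675, power 0.75
- m = 20%: 0.60, power 0.34

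**The case against.** The direction is inferred, not shown. A responder who skips month 12 for unrelated reasons pulls the estimate down, and 0.44 is the extreme corner in which none of the removed patients responded. The 20% is attrition among patients accrued. Section 5.7.1 includes reasons that arise before treatment, such as osteonecrosis on the pre-procedural MRI, and others with no clear link to response, such as pregnancy. The share removed for outcome-related reasons may therefore be well below 20%. All of this stands, and it is why a range of q and a smaller d are shown.

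A reader might infer that the set strips out treatment failures generally. It does not. A non-responder who attends every visit stays in as a failure, and Sections 3.1 and 10.4.1 already count increased pain medication or injection as failure. An adverse event permits discontinuation; it does not by itself remove anyone.

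A reader might also infer that the optional visit 8 is needed for inclusion. The Protocol Summary and Section 5.5 name month 12 as the last follow-up, so this is only an ambiguity of wording. Nor do the documents show that replacement would breach the 50-subject limit: the plan states accrual of 50 and does not say that replacements come on top.

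Finally, this is a pilot. But it sets a formal hypothesis, a 5% level and a decision rule, and those need an analysis set that is not selected after the endpoint. Nothing in the objection justifies discarding valid 3-month scores.

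**Conclusion.** The defect is established from the text. The sole analysis set ties a 3-month endpoint to attendance through month 12, discards valid primary outcomes and does not match the treated population named in the conclusion. It should be corrected before database lock.

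Upward bias is likely, because of the withdrawal reasons and unrestricted replacement, but its size cannot be fixed from the documents. At a true rate of 50% with the planned 20% removed, the completer rate is at most 12.5 points too high, and the false-positive rate runs from 0.44 (no removed patient responded) through 0.040 (no bias) to 0.006 (75% responded). These figures rest on an assumed q, on the assumed 26/40 cut-off, and on all attrition falling after treatment.

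**What to change.** Rewrite Section 10.3 as follows.

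- Primary set: all patients in whom embolization was attempted, using every observed 3-month outcome whatever happens later.
- Count as non-responders those who have knee surgery, or withdraw for an adverse event or lack of benefit, before the 3-month assessment.
- Handle other missing 3-month scores by a rule stated in advance, with a tipping-point analysis that includes the case of all missing as failure.
- Keep treated patients who are replaced in the denominator, and state how replacement fits within the 50-subject limit in Section 2.2.
- Report completers as supportive only, and state that visit 8 does not affect inclusion.
- Give the exact cut-off for the actual n: 26/40, 29/45 or 32/50 (one-sided alpha 0.040, 0.036 and 0.032).

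The work is protocol wording and one sensitivity analysis. The reported success rate may be somewhat lower. If every missing score is made a failure in the primary analysis, the power loss in step 4 is real, which is why that case is better placed within the tipping-point analysis than imposed as the only rule.

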10.4 Description of Statistical Methods

The response rate will be summarized in terms of the observed proportion of patients manifesting a positive response and a two-sided exact 95% confidence interval (CI) per the Blyth-Still-Casella method (31).

10.4.1 General Approach

This is a single arm study (i.e., no sham, placebo or alternative treatment included). The primary objective (clinical success rate) will be assessed as a binary outcome of whether or not each patient shows at least a 50% reduction in WOMAC pain scores from baseline (pre-treatment) to post-treatment follow-up at 3 months without an increase in baseline incidence of pain medication use or intra-articular injection. The response rate will be summarized in terms of the observed proportion of patients manifesting a positive response and a two-sided exact 95% confidence interval (CI) per the Blyth-Still-Casella method. WOMAC pain score, pain VAS, WOMAC stiffness and physical activity scores will be assessed as mean and standard deviation.

10.4.2 Analysis of the Primary Endpoint(s)

The primary endpoint is the clinical success rate defined as at least 50% reduction in WOMAC pain score at 3-month follow-up compared to baseline as a binary assessment.

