Interventional Template Version: 12 February 2020

US	United States
UP	Unanticipated problem
VAS	Visual analog scale
WOMAC	Western Ontario and McMaster Universities Osteoarthritis index
WOMRS	Whole-Organ Magnetic Resonance Imaging Score

CONFIDENTIAL

Protocol Summary

[figure not shown]
Title	Genicular Artery Embolization for Treatment of Knee Osteoarthritis (OA)
Short Title	Geniculate Artery Embolization for Treatment of Knee Osteoarthritis
Brief Summary	Single-arm, single-center, no sham or placebo, prospective pilot trial designed to evaluate the feasibility and safety of transcatheter arterial embolization in patients with knee OA. Eligible participants will receive geniculate artery embolization using Embosphere™ Color-Advanced Microspheres. Patients will be followed up for a total of 12 months.
Objectives	Primary objective: to determine the effectiveness of genicular artery embolization in reducing knee pain at 3-months post intervention in patients with knee OA. This will be assessed by evaluating the clinical success rate defined as at least 50% reduction in Western Ontario and McMaster Universities Osteoarthritis index (WOMAC) pain score from pre-intervention baseline to follow-up visit at 3 months post-intervention without an increase in baseline incidence of pain medication use or intra-articular injection. The WOMAC Score will be calculated from the Knee injury and Osteoarthritis Outcome Score (KOOS) score. Secondary objectives: 
 - To evaluate the safety of genicular artery embolization - To determine whether transcatheter arterial embolization improves OA-related knee symptoms and quality of life.
Methodology	Prospective, single-arm, single-center, no sham or placebo, pilot study
Endpoint	Primary endpoint: WOMAC pain score at 3-months post intervention. Secondary endpoints: 
 - Rate, type, causality, and severity of adverse events - WOMAC pain score at 1-, 12-, and > 12-months post intervention - Pain visual analog scale (VAS) - WOMAC knee stiffness and physical function scores at 1, 3, 12 months
Study Duration	3 years
Participant Duration	Each individual subject will be enrolled for approximately 13 months to complete all study visits from the initial screening visit to last follow up at 12-months post intervention. Participants that completed the 12 months visit by August 31, 2024 will be invited to participate in longer follow up (18 months – 48 months follow-up).

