3.1 Primary Objective

The primary objective of the study is to determine the effectiveness of genicular artery embolization in reducing knee pain at 3-months post intervention in patients with knee OA. This will be assessed by evaluating the clinical success rate defined as at least 50% reduction in WOMAC

CONFIDENTIAL

pain score from pre-intervention baseline to follow-up visit at 3 months post-intervention without an increase in baseline incidence of pain medication use or intra-articular injection.

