4.1 Description of Study Design

This study is a single-center, single arm, no sham or placebo, open label, prospective pilot study designed to evaluate the safety and feasibility of geniculate artery embolization for the treatment of knee OA. Enrolled patients will receive angiography and embolization of the one or more geniculate arteries in the affected knee using 250 µm Embosphere microspheres. If both knees are affected, the knee with the higher pain score on electronic VAS will be targeted.

The primary objective is to evaluate the effectiveness of geniculate artery embolization in reducing knee pain at 3 months. The primary objective will be evaluated by the clinical success rate. Clinical success is defined as at least 50% reduction in WOMAC pain score at 3-month follow up visit. 40 patients will be required for this study. The study would accrue 50 patients to account for an attrition rate of 20%.

Change in WOMAC pain score and pain VAS will be used as a measure of efficacy (i.e., pain reduction).

WOMAC questionnaire is a widely used, disease-specific measure for knee OA. It includes 24 questions on daily activities. WOMAC pain score includes five questions regarding pain (pain during walking, stair climbing, nocturnal, rest, weight bearing); each question will be scored using the

CONFIDENTIAL

following points: 0 for no pain, 1 for mild, 2 for moderate, 3 for severe, and 4 for extreme pain. possible score ranges for pain are 0–20. For this purpose, WOMAC Score will be calculated from the Knee injury and Osteoarthritis Outcome Score (KOOS) score which was developed as an extension of the WOMAC score with the purpose of evaluating short-term and long-term symptoms and function in subjects with knee injury and osteoarthritis. This means that the KOOS questionnaires will be administered to patients during visits and the WOMAC score will be calculated from the KOOS scores later at the time of data analysis.

The electronic VAS is a horizontal line with no markings on the scale except “No pain” on the left (score: 0 mm) and “worst possible pain” on the right end of the scale (score: 100 mm). Subjects mark the VAS to indicate their current pain level, with 0 mm representing “No pain” and 100 mm representing “worst possible pain”. In our study, subjects will be asked to mark their pain level on a paper VAS on study questionnaire form and will give a score between 0 to 100, which will be documented on the appropriate eCRF.

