4.2 Study Endpoints

4.2.1 Primary Study Endpoints

The primary endpoint is WOMAC pain score at 3 months post intervention.

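### Clinical success at 3 months is defined both with and without a medication and injection condition, and nothing planned settles which definition the primary test uses

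*Combined protocol and SAP*

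**What the plan says.** Two responder definitions are in the current text.

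- **Pain only.** Section 10.4.2: "The primary endpoint is the clinical success rate defined as at least 50% reduction in WOMAC pain score at 3-month follow-up compared to baseline". Section 10.2, which holds the hypothesis and the decision rule, says the primary objective "is a binary assessment of whether or not each patient shows at least a 50% reduction in WOMAC pain scores from baseline". Section 4.1: "Clinical success is defined as at least 50% reduction in WOMAC pain score at 3-month follow up visit".
- **Composite.** Section 3.1 requires the reduction in "pain score from pre-intervention baseline to follow-up visit at 3 months post-intervention without an increase in baseline incidence of pain medication use" and extends the condition to intra-articular injection. The Objectives row of the Protocol Summary says the same. Section 10.4.1 assesses the outcome at "follow-up at 3 months without an increase in baseline incidence of pain medication use or intra-articular injection".

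A third label appears without any threshold. Section 4.2.1: "The primary endpoint is WOMAC pain score at 3 months post intervention". The Endpoint row of the Protocol Summary: "Primary endpoint: WOMAC pain score at 3-months post intervention".

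Section 10.2 tests a null proportion of 0.5 against 0.75, one-sided, and rejects with 16 or more responders among 23. Section 10.5 gives 80.4% power at a realized level of 0.047 and says the sample size was first chosen on the primary objective. Section 10.1 states that no formal SAP will precede database lock.

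**The concern.** Sections 10.4.1 and 10.4.2 are consecutive and classify some patients differently. A patient whose pain score halves, but who takes more analgesics than at baseline or has an injection during follow-up, is a success under 10.4.2 and a failure under 10.4.1. I found nothing that bars such changes; 7.4 asks only that they be recorded.

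The choice of definition can therefore decide the primary result. With no SAP planned, no blinding, and statistical analysis assigned in Section 1 to an investigator who also performs the procedure, it could be made after the responses are known. The condition is also not operational: no drugs, look-back window or threshold are attached to it, and incidence is normally a group-level quantity rather than a property of one patient.

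**Working it through.** **Inputs from the plan.** Null 0.5, alternative 0.75, one-sided, reject at 16 or more of 23 (10.2); nominal level 5%, power 80.4%, realized level 0.047 (10.5).

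**1. The stated design reproduces.** With X binomial(23, p):

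- Level: P(X ≥ 16 | 0.5) = 390,656 / 2^23 = 390,656 / 8,388,608 = 0.0466, which rounds to 0.047.
- Power: P(X ≥ 16 | 0.75) = 0.8037, that is 80.4%.

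**2. One discordant patient, with no outside assumption.** Suppose 16 of 23 patients halve their pain score and one of them fails the medication or injection condition.

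- Pain only: 16/23, p = 0.0466, reject.
- Composite: 15/23, p = (390,656 + 490,314) / 8,388,608 = 880,970 / 8,388,608 = 0.105, do not reject.

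**3. Power, if 0.75 is the pain-only rate.** The documents give no rate of failing the condition. Assume a share f of pain responders fails it. The composite rate is then 0.75 × (1 − f). Every composite responder is also a pain responder, so the chance that pain-only passes while the composite fails is the difference between the two powers.

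| f (assumed) | Composite rate | Composite power, 16/23 | Pain-only passes, composite fails |
|---|---|---|---|
| 5% | 0.7125 | 0.668 | 0.804 − 0.668 = 0.135* |
| 10% | 0.675 | 0.515 | 0.804 − 0.515 = 0.289 |
| 20% | 0.60 | 0.237 | 0.804 − 0.237 = 0.566* |

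*From unrounded values: 0.8037 − 0.6683 = 0.1354 and 0.8037 − 0.2373 = 0.5664.

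If 0.75 was instead meant for the composite, the 80.4% already belongs to it and this loss does not arise.

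**4. False positives, if the composite is the intended target.** With the true composite rate at 0.5, the pain-only rate is 0.5 / (1 − f): 0.526, 0.556 or 0.625 for the same values of f. Testing pain-only at 16/23 then rejects with probability 0.077, 0.126 or 0.320, against the stated 0.047.

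**5. The condition is open to more than one reading.** Section 5.2 excludes patients with an injection in the target knee in the preceding 3 months, while 7.1.1 records injections over 12 months. Take a patient injected once 6 months before baseline and once after the procedure. The count rises from 0 to 1 on a 3-month look-back, but is 1 against 1 if a 12-month history is the comparator.

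**The case against.** The best defence is that the short form is shorthand. Section 10.2 presents its binary measure as the clinical success rate of the primary objective, which 3.1 defines with the condition, and 10.4.1 repeats the condition in full. That reading is possible. But 4.1, 10.2 and 10.4.2 each spell out a complete criterion without referring back, and 10.4.2 is the section headed as the primary endpoint analysis. An analyst following it would not apply the condition.

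The defence is stronger on power. Section 10.5 ties the sample size to the primary objective, and 10.2 and 10.5 describe the tested proportion only as patients with a positive treatment response. The 0.75 may have been meant for the composite, so the figures in step 3 are conditional.

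Pain medication must be withheld for 24 hours before each pain assessment (7.3, 7.4). This partly limits the effect of added analgesics on the score. It does not address injections, and it does not settle the definition.

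The share f is an illustration without an anchor in the documents; step 2 needs no such share.

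**Conclusion.** The conflict is real and must be fixed before lock. Two definitions compete for one test, and under the stated rule a single discordant patient moves p from 0.047 to 0.105.

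Three stronger inferences are tempting and not supported:

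- **That there are three rival tests.** The raw 3-month score in 4.2.1 and the Summary has no threshold, hypothesis or decision rule. It can be read as the variable behind the responder rate. It is a labelling inconsistency and cannot itself pass or fail.
- **That the 80.4% power belongs to pain-only and is overstated for the objective.** The documents do not say which definition 0.75 refers to. The fall to 0.67, 0.51 or 0.24 rests on two assumptions: that 0.75 is the pain-only rate, and that 5%, 10% or 20% of pain responders fail the condition.
- **That a particular count out of 40 passes or fails.** The plan now calls for data from 40 patients but states a rule only for 23. An exact 5% cut-off for 40 can be derived (26/40, p = 0.040; 25/40, p = 0.077) and is equally sensitive to one patient, but it is not the protocol's rule.

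Nor do the documents show that anyone intends to choose the definition after the fact. The point is that nothing planned prevents it.

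**What to change.** 1. State one primary endpoint, in identical words, in the Protocol Summary (Objectives and Endpoint rows), 3.1, 4.1, 4.2.1, 10.2, 10.4.1 and 10.4.2. The composite of 3.1 and 10.4.1 is the natural choice, because 10.5 bases the sample size on the primary objective.
2. Make the condition a patient-level rule using data already collected: which drugs count, the look-back window at baseline and at 3 months, what counts as an increase, and how injections are compared with baseline. The drug classes and 30-day window that 3.2 lists for the secondary medication objective are a possible starting point.
3. Name the other responder rate and the mean 3-month change in WOMAC pain as supportive analyses.
4. State in 10.5 which definition the 0.75 rate and the power refer to.
5. Record all of this in a dated document before database lock, including which outcome data were already known.

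**Cost.** No new visits or measurements are needed. If 0.75 was meant for pain-only, the power stated for the composite becomes lower. The late visit is offered to participants who completed 12 months by August 31, 2024, so 3-month results may already have been seen. In that case rewording cannot fully restore prespecification, and both rates must be reported.
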